6.3.1.3 Sensitivity analysis

In order to out-balance the fact that the "high"-risk stratum has primary outcome measures every third month we will perform a sensitivity analysis on the primary endpoint. Any primary endpoint in the "high"-risk stratum between annual visits will be carried forward to the date of the following annual visit. This analysis is most likely underpowered because of exclusion of endpoints in the high-risk stratum, however, the trend of the primary analysis is expected.

As in the "high"-risk group we have participants allocated to either active IMP or placebo we potentially limit the number of endpoints if the active IMP is beneficial. To adjust for this potential effect, we will perform a sensitivity analysis on the primary endpoint only in "low"-risk participants and in "high"-risk participants allocated to placebo treatment. This analysis is most likely also underpowered because of exclusion of endpoints in the "high"-risk stratum, however the trend of the primary analysis is expected.

ANOVA models for each continuous variable measured at baseline: age, HbA_{1c}, systolic blood pressure, Study site, eGFR and UACR will be tested within each stratum "high"- and "low"-risk as well as interaction in the Cox-model between strata with the primary endpoint as determinant. Chi square tests will be used for categorical variables: gender, use of antihypertensive agents, known cardiovascular disease and retinopathy.

We expect a correlation between the “high”-risk stratum and events of the primary endpoint for participants with known risk factors for overt kidney disease (higher age, HbA_{1c}, systolic blood pressure, UACR, and lower eGFR, male gender, use of antihypertensive agents, known cardiovascular disease and retinopathy).

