## **8 RANDOMIZATION/BLINDING AND UNBLINDING PROCEDURES**

### **8.1 Patient Identification**

All patients included into the screening process will receive a consecutive patient number, starting with patient number 0001. The patient identifier is the combination of the study site number (e.g. 01) and the patient number (e.g. 0001).

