3.2 Randomization

At baseline eligible patients with a high-risk proteomics pattern will be included in the intervention part of the study. Randomization lists will be prepared by an independent statistician at the Robertson Centre, University of Glasgow, who is not involved into other tasks of the trial.

The patients will be randomly assigned in a 1:1 ratio to one of the two treatment arms using a block randomization stratified by study center.

Patients will be stratified in the two treatment arms (1:1) based on whether or not the patients is treated with RAS blocking agents at the time of entry (Screening) in order to have the number on RAS blocking agents balanced in the two treatment arms.

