5.3.3 Site

15 sites in 10 countries were active recruiting.

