6.3.2.2 Analysis of secondary endpoints

Based on a 2x2 table included the primary endpoint (event/ event free) vs. treatment allocation (active/ placebo) we will calculate numbers needed to treat and tested for significance using Chi-square test.

For Cox-regression models both unadjusted and adjusted using treatment allocation as determinant. Adjustment for age, gender, HbA_{1c}, systolic blood pressure, retinopathy, study site, eGFR and UACR at baseline will be conducted for both primary and secondary endpoints (see section 6.1.1 and 6.1.2, excluding 6.1.2 C, H and J).

For further clarification of the added value for discrimination, the rIDI will be calculated for all above described Cox-regression models with a significant HR for treatment allocation in the unadjusted model for each endpoint.

For safety outcome (section 6.2.1 J) only AE/SAE with the term hypotension, hyperkalaemia or gynaecomastia will be analysed using chi-square test.

To evaluate changes in UACR and eGFR over time (outcome measurement C and H in section 6.2.1) a linear mix model will be applied with adjustment for eGFR and UACR at baseline.

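### SAP 6.3.1.3 lists study site as a continuous variable; run as written, the site check depends on arbitrary site numbers and loses much of its power

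*SAP*

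**What the plan says.** SAP 6.3.1.3 (sensitivity analysis of the observational cohort) announces "ANOVA models for each continuous variable measured at baseline". It then lists age, HbA1c, systolic blood pressure, study site, eGFR and UACR: "systolic blood pressure, Study site, eGFR and UACR will be tested within each stratum". The whole list is tested within the high-risk and low-risk strata, "as well as interaction in the Cox-model between strata with the primary endpoint as determinant". A separate list follows: "Chi square tests will be used for categorical variables: gender, use of antihypertensive agents, known cardiovascular disease and retinopathy". Site is not in it.

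Other places show what kind of variable site is:
- Protocol 8.1: "The patient identifier is the combination of the study site number (e.g. 01) and the patient number (e.g. 0001".
- SAP 5.3.3: "15 sites in 10 countries were active recruiting".
- SAP 3.2: allocation is made "using a block randomization stratified by study center".
- SAP 6.3.2.2, for the intervention cohort: "Adjustment for age, gender, HbA_{1c}, systolic blood pressure, retinopathy, study site, eGFR and UACR at baseline will be conducted". No coding for site is given.

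Neither document says that site is to be declared a class variable.

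**The concern.** The other five variables in the list are properly continuous. Site is an identifier, so its mean, variance and linear trend have no meaning.

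SAP 6.3.1.3 is the only place where site enters the SAP's observational analysis. The adjustment sets in SAP 6.3.1.1, 6.3.1.2 and 6.4 leave it out. It is also the only planned test in either document of whether the CKD273 contrast is the same across sites. The primary objective is to confirm the proteomic test in a multicentre cohort, and site differences are plausible: sites collect, dipstick-test, freeze and ship the urine (Protocol 10.9 and 10.10), and background care follows local guidelines (Protocol 6.2 and 12.3). A check that depends on how sites were numbered would give weak reassurance if negative and could not be interpreted if positive.

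**Working it through.** **Plan's own figure.** The documents give no figure for the site check. The event proportions used below come from SAP 3.4, where 129 per arm is reproduced by the unpooled two-proportion formula: (1.960 + 0.842)² × (0.40×0.60 + 0.24×0.76) / (0.40 − 0.24)² = 7.849 × 0.4224 / 0.0256 = 129.5.

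**Inputs.** Cohort 1811 (SAP 2.3.1); high-risk share 15% (Protocol 15.1); 15 sites (SAP 5.3.3); event proportions 24%, 40% and 8.5% (SAP 3.4); alpha 0.05 (SAP 4.1). Between-site SDs are assumptions.
- High-risk: 0.15 × 1811 = 272. Low-risk: 1811 − 272 = 1539.
- High-risk event proportion over both arms at 1:1: (0.40 + 0.24)/2 = 0.32.
- Expected events: 272 × 0.32 = 87 high-risk, or 87/15 = 5.8 per site; 1539 × 0.085 = 131 low-risk, or 131/15 = 8.7 per site.

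**Step 1: what the text specifies.** With the primary endpoint as determinant, each listed variable is the ANOVA response and event status is the grouping factor. For site, this compares mean site numbers. As an illustration, one simulated data set of 1811 patients (strata pooled, SD of log risk 0.35, 14-df p < 0.0001) was renumbered 3000 times. The ANOVA p-value ran from below 0.0001 to 1.0, and 47% were below 0.05.

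**Step 2: share of between-site variation captured.** For k equal-sized sites in random order, a linear term captures on average 1/(k − 1) of the variation: 1/14 = 7.1% for k = 15. With normal site effects the share follows Beta(1/2, 13/2); its median is about 3.6%, and it exceeds 25% in about 6% of numberings. For the roughly 17 centres in the protocol synopsis the average is 1/16 = 6.3%. This step needs no assumed SD.

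**Step 3: general power.** Find the noncentrality λ that gives the 14-df chi-square test a stated power, then average the power of the 1-df test with noncentrality λR² over the distribution of R² in step 2.

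| 14-df power | λ | Mean power, site code |
|---|---|---|
| 80% | 18.34 | 20% |
| 90% | 23.02 | 23% |
| 99% | 35.81 | 31% |

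**Step 4: within stratum, as the SAP plans.** Simulation with 15 unequal sites and site effects on the log-hazard scale:

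| Stratum | SD | 14-df test | Site code |
|---|---|---|---|
| Low-risk | 0.2 | about 23% | about 9% |
| Low-risk | 0.35 | about 63% | about 19% |
| Low-risk | 1.0 | about 99% | about 54% |
| High-risk | 0.2 | about 13% | about 9% |
| High-risk | 0.35 | about 44% | about 16% |
| High-risk | 1.0 | about 98% | about 40% |

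The scale matters in the high-risk stratum. With an SD of 0.35 on log risk instead of log hazard, the figures are about 66% against 21% (low-risk) and 62% against 21% (high-risk).

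**Step 5: site-by-CKD273 interaction.** Poisson approximation to Cox, 500 replicates per setting:

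| SD | Factor, 14 df | Site code, 1 df |
|---|---|---|
| 0 | 7.6% | 4.8% |
| 0.3 | 28% | 11% |
| 0.5 | 65% | 20% |
| 0.7 | 90% | 28% |
| 1.0 | 99% | 44% |

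The SD 0 row is the type I error. The site code holds its level, so the fault is lost power and arbitrariness, not false positives. The factor test runs above 5% because events per site are few, so its power is slightly flattered.

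**The case against.** The strongest reply is that this is a list slip. Elsewhere site is treated as a grouping variable: it stratifies the randomization, and SAP 6.3.2.2 lists it beside gender and retinopathy. The sentence in 6.3.1.3 is loosely built, and a programmer may well declare site as a class variable without being told. That is fair, and it is why the point is conditional on following the text as written. But a class declaration can rescue only the Cox interaction. It cannot rescue the ANOVA, where a nominal label would be the response.

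A reader might infer that the check would miss most real site differences. The documents do not support so flat a statement, because they give no between-site SD. In a model pooled over both strata, the site code misses 77% and 57% of main effects at SD 0.3 and 0.5, but only 41% and 29% at 0.7 and 1.0. For the interaction it misses 56% to 89% over SD 0.3 to 1.0, but at SD 0.3 the categorical test itself misses 72%.

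Two further points stand in the plan's favour. Proteomic analysis is done at one laboratory and UACR is measured centrally (Protocol 10.9 and 10.10), which limits the sources of site difference. Protocol 15.6 also plans Cox adjustment for center; that addresses differences in baseline risk, though not whether CKD273 performs alike across sites.

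**Conclusion.** The point holds as a minor one. SAP 6.3.1.3 assigns a 15-level label to the wrong variable type, and the site check as specified is arbitrary. The 7% average share rests only on the number of sites and random numbering of equal-sized sites. The power figures rest on the assumed SDs, the planning event proportions and the assumed site sizes. Across them the site code is the weaker test, by a small margin when heterogeneity is slight (9% against 13% in the high-risk stratum at SD 0.2) and by a wide one when it is moderate or large.

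A reader might also infer that the main comparison is compromised. It is not. The primary Cox analyses in SAP 6.3.1.1 and 6.3.2.1 do not use site, no decision rule hangs on this check, and sample size and type I error are unchanged.

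**What to change.** 1. In SAP 6.3.1.3, move study site to the categorical list: a chi-square or Monte Carlo exact test of site by event within each risk stratum.
2. Specify the site-by-CKD273 test in the Cox model as a random site-by-risk effect, or as a categorical factor with small sites pooled by a rule fixed before unblinding. The rule is needed because only about 6 high-risk events per site are expected.
3. In SAP 6.3.2.2, state that site enters the adjusted Cox models as a categorical variable or as a stratum.

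The cost is a few sentences in the SAP, with no new data. The downside is that the categorical interaction test still has low power at modest heterogeneity (28% at SD 0.3), so a non-significant result should not be read as proof that the test performs alike at every site.

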6.3.2 Intervention study (Intention to treat cohort)

6.3.2.1 Primary analysis of primary endpoint

In the intention to treat cohort, a comparison between active and placebo treatment will be performed in a Cox-regression model including data on the primary outcome. Adjustments in the model will only be performed for eGFR and/or UACR in the case of a significant unbalance in the baseline value (significance level for unbalance between treatment allocation groups is a p-value < 0.01).

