	
The expected relative proportions of diabetes type 2 patients developing microalbuminuria in our study population are: 24% in patients at high-risk for diabetic nephropathy in the treatment group, 40% in those patients at high-risk for diabetic nephropathy in the placebo group and 8.5% in those therapy-naive patients at low-risk for diabetic nephropathy. Using the samples size formula for two proportions test (<math>\alpha=0.05</math> <math>\beta=0.80</math>), randomized (1:1), <math>n=129</math> in each arm of the intervention group. To account for drop-outs we plan to randomize 300 in all. It is expected that approx. 15% of the population will show a pattern of high-risk of CKD, therefore 2000 patients have to be included. Equal drop-out frequency is expected in both groups and there will be no replacement of drop-out. Discontinuation prior randomization is categorized screening failure.
 
Analysis populations: The primary analysis will be conducted for all patients included (intent-to-treat population) in the observational and intervention study groups. In addition, all relevant efficacy endpoints will be also analyzed for the per protocol population in both study groups.
 
Analysis of primary endpoint: Cox regression analysis of development of the primary endpoint adjusted for age, gender, study site will be conducted in both study groups (observational and intervention) and for study intervention in the interventional group. Secondly adjusted in addition for baseline UACR, HbA1c and BP.
 
Analysis of secondary endpoints: Cox regression analysis of development of secondary endpoints in the both study groups (observational and intervention) as well within the interventional group (high- vs. low-risk), adjusted for age, gender, study site and study intervention with secondary adjustment for baseline UACR, HbA1c and BP.
 
Assessment of safety: The assessment of safety will be based primarily on the frequency of eCRF-documented AEs, laboratory abnormalities, and SAEs (see section 13.3). Occurrence and frequency of eCRF-documented AEs, SAEs and laboratory abnormalities will be summarized by treatment group.
 
In addition AEs leading to death and AEs leading to discontinuation of study medication and/or withdrawal will be summarized for the two treatment groups.
 
Final analysis plan: Statistical analysis of the data will be performed by Steno Diabetes Center. A statistical analysis plan will be written and signed before database lock and unblinding of the entire treatment code.
 
Methods for imputation and type of censoring will be clarified in the statistical analysis plan prior to database lock and unblinding.

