## 15.6 Analysis of primary endpoint

The primary endpoint is defined as time to the first occurrence of microalbuminuria (UACR >30 mg/g and <300 mg/g) in 2 out of 3 sterile first morning void urine samples with a geometric mean of UACR >30% above initial geometric mean UACR OR geometric mean > 40 mg/g in three samples. The baseline urinary albumin-to-creatinine ratios are the geometric mean of three measurements obtained during the "run-in" period.

It is expected, that the number of patients who will drop out between randomization and occurrence of microalbuminuria will be low (<15%).

If those cases where drop out occurs before sampling during the study period, prior to unblinding the treatment code it will be specified in the statistical analysis plan, whether these patients have to be considered as a treatment failure in the analysis of the primary endpoint.

The predictive value of a positive and negative test, specificity and sensitivity of the test in relation to prediction of development of the primary endpoint will be evaluated. To assess whether CKD273 classifier (the marker) improved risk prediction of the primary outcome we determined the concordance statistic (c-statistic) and Integrated Discrimination Improvement (IDI). Both parameters measure the discriminative ability of a marker in a model to distinguish between people who will or will not develop the outcome (in case of predictive methods).

The primary endpoint will be analyzed in the total population with comparisons of high- vs. low-risk pattern and active vs. placebo treatment using a Cox proportional-hazards regression model with treatment as a fixed effect; the baseline urinary albumin-to-creatinine ratio will be logarithmically transformed (base 10) as a covariate, and a two-tailed Wald chi-square test with an alpha level of less than 0.05; hazard ratios and two-sided 95 % confidence intervals will be calculated. Kaplan Meier plots of the groups will be made.

Secondly, the analyses will be adjusted for age, gender, center, HbA1c and BP. Thirdly, further adjustment for any baseline demographic variables which are significantly different between the groups and related to albuminuria at baseline will be calculated. In addition adjustment will be made for significant changes in RAAS blockade or treatment with aldosterone receptor antagonist as concomitant medication during the study period.

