2.3 Objective

2.3.1 Primary objective

To confirm that urinary proteomics can predict development of microalbuminuria (as a surrogate marker for the development of overt nephropathy) in a cohort of 1811 type 2 diabetic patients with normal urinary albumin excretion.

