2.3.2 Secondary objectives

To investigate if early initiation of preventive therapy with spironolactone 25 mg once daily reduces risk of transition to microalbuminuria in those patients identified by urinary proteomics to be at high risk.

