4 STATISTICAL PRINCIPALS

4.1 Confidence limits and significance level

Any p-value below 0.05 will be considered statistically significant. A p-value will be calculated for the primary analysis. P-values for the secondary analyses will only be calculated if the primary analysis yields a p-value below 0.05. For all primary and secondary analyses 95 % confidence limits will be calculated.

Continuous values fulfilling terms of normal distribution will be displayed as mean values and 95 % confidence limits of the mean. Variables not fulfilling terms of normal distribution will be displayed as median and inter quartile range from p25 to p75.

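### The primary spironolactone-versus-placebo Cox model adjusts for baseline UACR only if a baseline test gives p < 0.01, while the protocol states two other primary models

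*SAP*

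**What the plan says.** Three first models are given for the same active-versus-placebo comparison of the primary endpoint.

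- **SAP 6.3.2.1:** a Cox model without covariates, except that "Adjustments in the model will only be performed for eGFR and/or UACR in the case of a significant unbalance in the baseline value". Imbalance counts as significant at p < 0.01. Neither the test nor the UACR scale is named.
- **Protocol 15.6:** a Cox model with treatment in which "the baseline urinary albumin-to-creatinine ratio will be logarithmically transformed (base 10) as a covariate", with no condition attached and a two-tailed Wald test. Age, gender, centre, HbA1c and BP enter in a second step.
- **Protocol synopsis:** "Cox regression analysis of development of the primary endpoint adjusted for age, gender, study site" comes first. Then: "Secondly adjusted in addition for baseline UACR", together with HbA1c and BP.

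SAP 6.3.2.2 does plan an unconditional model for the primary endpoint that includes UACR, eGFR and study site, but lists it among the secondary analyses. SAP 4.1 gives it an interval in any case: "For all primary and secondary analyses 95 % confidence limits will be calculated". Its p-value is conditional: "P-values for the secondary analyses will only be calculated if the primary analysis yields a p-value below 0.05". SAP 4.1 does not say which comparison is meant. The primary objective (SAP 2.3.1) is the risk comparison, "To confirm that urinary proteomics can predict development of microalbuminuria". The drug comparison, "To investigate if early initiation of preventive therapy with spironolactone 25 mg once daily reduces risk", is the secondary objective (SAP 2.3.2).

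**The concern.** A significance test of baseline balance is a poor way to choose covariates in a randomised trial. Any difference it finds is chance by design, and it says nothing about whether the covariate predicts outcome. Expected prognostic value is the better basis, and here it is plain. The endpoint is itself a UACR threshold: two of three voids above 30 mg/g, with either a 30% rise or a geometric mean above 40. SAP 6.3.1.3 and 6.3.2.3 also class UACR as an established risk factor.

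Three things are at stake: the power that adjustment would add, the dependence of the primary p-value on chance UACR imbalance, and clarity about which of three models gives the primary result if they disagree.

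**Working it through.** **1. The plan's own sample size.** Inputs from SAP 3.4: 40% vs 24%, α = 0.05 (two-sided, protocol 15.6), power 0.80 (written there as β), 1:1 allocation.

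n per arm = (1.960 + 0.842)² × (0.40×0.60 + 0.24×0.76) / 0.16² = 129.5, which matches the stated 129. Then 258 / 0.90 = 287, so 300 covers 10% drop-out. No covariate is involved, so the planned 80% does not depend on adjustment.

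**2. How often the rule acts.** Randomisation is stratified by centre and RAS blockade (SAP 3.2), not by UACR. A valid 1% test therefore fires in 1% of trials for UACR, and for either covariate in 1 − 0.99² = 2.0%. Simulation gave 0.95–1.01% and 1.9–2.0%.

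The largest standardised difference that does not trigger is t(0.995) × √(2/n): 0.30 SD at 150 per arm and 0.32 SD at 129. If the hazard ratio (HR) per SD of log UACR is 2, such a difference alone shifts the treatment HR by a factor of 2^0.30 = 1.23 to 2^0.32 = 1.25. At 1.5 per SD the factor is 1.13–1.14.

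**3. Power.** The implied treatment HR is ln 0.76 / ln 0.60 = 0.537. With about 91 events, power = Φ(√91/2 × 0.621 − 1.96) = Φ(1.00) = 84%.

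The simulation used 300 patients, follow-up uniform over 2–4.4 years, exponential event times and 10% drop-out, marginal risks fixed at 40% and 24%, and 20,000 trials per row. The prognostic strength of UACR is assumed. The last two columns are trials with UACR imbalance at p 0.01–0.10, about 9% of trials in all and about 4.4% in each direction.

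| HR per SD of log UACR | Unadjusted | UACR-adjusted | Active arm higher: unadjusted vs adjusted | Active arm lower: unadjusted vs adjusted |
|---|---|---|---|---|
| 1.0 | 83.7% | 83.6% | – | – |
| 1.5 | 84.1% | 86.0% | 75% vs 86% | 92% vs 85% |
| 2.0 | 84.3% | 89.9% | 61% vs 89% | 96% vs 89% |
| 2.5 | 84.5% | 93.5% | 56% vs 94% | 97% vs 92% |

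The p < 0.01 rule stays within 0.2 points of the unadjusted column. Overall type I error is 4.8–4.9% for both models. The treatment HR, unadjusted vs conditional on UACR, is 0.53 vs 0.52, 0.50 and 0.48 at 1.5, 2.0 and 2.5. A second simulation (135 per arm, 3,000 trials each) gave, for the SAP rule vs always adjusting, 81% vs 81%, 81% vs 83%, 82% vs 88% and 85% vs 95% at 1.0, 1.5, 2 and 3 per SD.

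**4. Simulating the endpoint rule itself.** The run above assumes that the fitted Cox model is true. A further simulation applied the entry limit, triplicate samples every 13 weeks and the actual event rule. It used seven assumed settings: median UACR 5–12 mg/g, between-patient log SD 0.4–0.7, day-to-day log SD 0.35–0.5, visit log SD 0.25–0.5, slope SD 0.25–1.2 per year. The resulting HR per SD was 1.2–2.9. In five of the settings, power was 93–96% adjusted with a robust standard error (SE), against 89–92% unadjusted, a gain of 1–7 points; stratifying by UACR quartile gave 93–97%.

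Type I error under three sets of assumed values:

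| Assumed values | Unadjusted | Adjusted, model-based SE | Adjusted, robust SE |
|---|---|---|---|
| Five of the settings above | 4.7–5.0% | 5.3–8.2% | 4.5–6.1% |
| Another five settings | 4.7–5.2% | 5.1–7.3% | 5.0–5.6% |
| A further four settings | 4.6–5.6% | 5.2–6.2% | 5.2–6.4% |

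Stratification by UACR quartile gave 4.4–5.2% in the first set.

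**5. Does eGFR belong too?** With UACR at 2.0 per SD, and eGFR independent of it, power without vs with eGFR is 90.2% vs 90.0%, 89.8% vs 90.6% and 90.3% vs 92.3% at eGFR HRs of 1.0, 1.25 and 1.5 per SD. The gain is at most about 2 points.

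**The case against.** The case for leaving the SAP alone is that its primary test is valid, holds 5% and meets the planned power. Dependence on chance imbalance is a feature of any unadjusted randomised comparison and is already counted in the 5%. The UACR-adjusted hazard ratio with its interval is pre-specified in SAP 6.3.2.2, and the forest plot in 6.3.2.3 splits by median UACR. Within the SAP the heading of 6.3.2.1 says which model is primary. All of this stands and limits the point to efficiency and clarity. It does not settle which document governs, because neither says that the SAP overrides protocol 15.6. Nor does any of these displays change the primary p-value.

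A second objection concerns the remedy. A robust SE appears in neither document, and under one set of assumed values it did not improve on the model-based SE (5.2–6.4% vs 5.2–6.2%). That is fair for those values. In the other two sets it brought the upper end down from 7–8% to about 6% or below. The benefit depends on how UACR behaves, and slight inflation may remain.

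Third, stratifying by UACR quartile was at least as well calibrated, with similar power. That also stands. The continuous covariate is preferred only because it is the protocol's own.

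Finally, the remedy leaves the randomisation factors, centre and RAS blockade, out of the primary model. So does the first model of protocol 15.6.

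**Conclusion.** The point holds. The p < 0.01 rule acts in about 1–2% of trials, so the SAP's primary treatment test is in effect unadjusted for a covariate on which the endpoint is defined, and it departs from protocol 15.6 without a stated reason. The documents give three candidate primary models.

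The loss is not one of validity. It is about 0–9 points of power for assumed hazard ratios of 1.0–2.5 per SD of log UACR, plus sensitivity to moderate imbalance: in about 9% of trials the SAP's rule ignores a UACR difference with p between 0.01 and 0.10. The conflict between the documents and the firing rate are certain. The size of the power loss rests on UACR distributions and prognostic strengths that the documents do not give. The change is worth making because it costs so little, but the trial does not fail without it.

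**What to change.** Replace the adjustment rule in SAP 6.3.2.1 with wording such as:

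> The primary model is a Cox regression with treatment and log10 baseline UACR (geometric mean of the run-in samples) as pre-specified terms, whatever the baseline balance. The treatment effect is the hazard ratio conditional on baseline UACR, with 95% CI and two-sided Wald p-value from a robust (sandwich) standard error. The unadjusted model and a model stratified by baseline UACR quartile are sensitivity analyses.

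Delete the p < 0.01 rule. State in advance that eGFR stays in the adjusted model of SAP 6.3.2.2 with age, gender and site. Including it as a second fixed covariate is also acceptable, but a baseline test must not decide. No RAS stratum is proposed here. A sponsor who prefers the quartile-stratified model as primary could defend that equally well, provided it is fixed beforehand.

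Before unblinding, reconcile SAP 6.3.2.1, protocol 15.6 and the synopsis, name the governing model, and state which comparison SAP 4.1 means by the primary analysis.

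The cost is SAP wording only: no extra patients, visits or data. Two things change in the report. The hazard ratio becomes conditional on baseline UACR and lies slightly further from 1, and its standard error is the robust one.
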